9.7.1.6.1 PRIMARY EFFICACY ANALYSIS

Primary analysis of primary endpoint

The primary analysis will be based on MCI/Prodromal subjects from the FAS with the prespecified censoring rule applied. The primary endpoint is the change from baseline to 18 months in the derived ADCOMS. The dose-response of the primary endpoint is modelled with a first-order normal dynamic linear model, where Normal and Inverse-Gamma priors are used. The primary efficacy analysis will calculate the Bayesian posterior probability that the dose identified is the most likely ED₉₀ dose that achieves 25% improvement over the placebo arm. At each interim analysis and the final analysis, 2 Bayesian probabilities will be summarized for each active dose: the probability it is the ED₉₀ dose and the probability of achieving 25% improvement over the placebo arm.

For the clinical efficacy data (ie, derived ADCOMS, MMSE, CDR, ADAS-cog, CBB, ISLT, and FAQ) subjects will be censored at the time of initiation of treatment with AChEIs or memantine, if they were not on these medications at the time of Baseline cognitive

assessment (Visit 2), and will be censored at the time of dose adjustment of AChEIs or memantine if they were already on stable treatment with these medications at the time of Baseline cognitive assessment (Visit 2). The value of the primary endpoint for censored subjects will be imputed using data up to the censoring time and Bayesian longitudinal modeling.

Sensitivity analysis of primary endpoint

After unblinding, the primary endpoint will be analyzed using the Bayesian methods described above as well as conventional statistical methods. The following additional Bayesian analyses will be conducted as sensitivity analyses:

- The primary endpoint will be analyzed regardless of initiation of treatment, or dose adjustment, with AChEIs or memantine using the same Bayesian analysis method as primary analysis. This is an intent-to-treat analysis without any censoring.
- In case of early success, the primary analysis as well as the above sensitivity analyses will be repeated after all subjects have completed 18 months of treatment or have been lost to follow-up.

Statistical methods for the final conventional analyses will use a mixed-effects model with repeated measures (MMRM) on the change from baseline in the derived ADCOMS at 18 months. The model will include treatment groups, randomization stratification variables (the presence or absence of ongoing treatment with AChEIs or memantine or both, and *ApoE4* status), and baseline ADCOMS as covariates. Other covariates such as adjusted hippocampal volume will be studied. These analyses will be performed as sensitivity analyses on the FAS as well as the PP set and as such, no multiplicity adjustments will be made to account for the interim analyses. In case of early success, the conventional analyses will also be performed using the data collected before the interim analysis.

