9.1.2.3 Follow-Up Period

All subjects, regardless of whether they complete all 18 months of treatment or discontinue study drug prematurely, will complete 4 post-treatment Follow-Up Visits: 2, 4, 8, and 12 weeks after the last dose of study drug. If clinically indicated, more frequent safety assessments can be conducted as part of unscheduled visits during the post-treatment Follow-Up Period. (revised per Amendment 04)

The end of the study will be defined as the date of the clinical database lock (ie, when all study data are collected and data validation is completed).

As required by some regulatory agencies, the following estimates are provided:

- The study will begin in Nov 2014 and is projected to end by Oct 2019 (end date will depend on actual recruitment rate).
- The maximum estimated period for each subject on study is anticipated to be approximately 2 years.

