9.7.1.1.1 PRIMARY ENDPOINT

- Change from baseline in the derived ADCOMS at 18 months of treatment in MCI/Prodromal subjects

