9.7.1.6 Efficacy Analyses

The MCI/Prodromal Cohort

The study in the MCI/Prodromal cohort is based on Bayesian adaptive design. Frequent interim analyses will be performed to assess the probability of early success and futility and to make early stopping decisions. Response adaptive randomization will be used to update the randomization probability among treatment groups at each interim analysis. Key definitions relevant to the Bayesian aspects of the adaptive design are given below.

Study Definitions

- **Maximum Effective Dose (d_{Max}):** The dose that achieves the greatest treatment effect.
- **ED₉₀:** The lowest dose that achieves at least 90% of the d_{Max} treatment effect in the derived ADCOMS.
- **Early Success:** The study in the MCI/Prodromal cohort will meet early success criteria if the probability that the ED₉₀ at 18 months of treatment achieves 25% improvement over placebo is at least 80%. Early success is achieved before all MCI/Prodromal subjects complete 18 months of treatment and can only be determined after at least 200 MCI/Prodromal subjects have been randomized. If early success is declared before

full randomization, the randomization of new MCI/Prodromal subjects will stop but subjects already randomized into the study will receive the full 18 months of treatment (following confirmation from the Sponsor's Senior Management).

- **Futility:** The study in the MCI/Prodromal cohort will meet statistical futility criteria if the probability that the ED₉₀ is better than placebo by the clinically significant difference of 25% is less than 5% at 18 months of treatment. The statistical futility boundary is binding; if the statistical futility boundary is crossed the study will be considered to have failed.
- **Study Success:** The study in the MCI/Prodromal cohort will be considered a success if an ED₉₀ at 18 months treatment has at least an 80% probability of achieving 25% improvement over placebo at either an interim analysis or at the final analysis.

The Mild to Moderate AD Cohort (revised per Amendment 01)

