If neither early success nor futility is reached and the study reaches full randomization, all subjects will complete 18 months of treatment. Interim efficacy analyses will be conducted every 3 months after full randomization is reached to assess futility and early success until all subjects complete 18 months of treatment. After full randomization, all study subjects will stop treatment only in the event of futility.

The DSMB will continue to monitor the safety aspects of the study throughout Stage A and Stage B. Details will be provided in the DSMB Charter. The study may be stopped for safety at any time.

The first Bayesian adaptive interim analysis will be conducted when 100 MCI/Prodromal subjects have been randomized into the study (ie, including MCI/Prodromal subjects from Stage A and Stage B). (revised per Amendment 01) Further interim efficacy analyses will be conducted after each additional 50 MCI/Prodromal subjects have been randomized, to a maximum of 500 MCI/Prodromal subjects (ie, at 100, 150, 200, 250, 300, 350, 400, 450, and 500 subjects randomized). If the study reaches full randomization, additional interim analyses will be conducted every 3 months until all subjects complete 18 months of treatment. The study will be monitored for futility at each interim analysis. Starting at the interim analysis for 200 subjects, the study will be monitored for success at each interim analysis. Each interim analysis will be conducted on data for the derived ADCOMS.

In addition, at each interim efficacy analysis, response adaptive randomization will be used to update the allocation of new subjects between placebo and active doses according to a predefined automated algorithm.

The Mild to Moderate AD Cohort (revised per Amendment 01)

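### If early success is declared, the complete 18-month analysis of the primary endpoint ranks only as a sensitivity analysis, and the protocol does not say which result prevails if it differs from the early look

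*Protocol*

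**What the plan says.** - **Endpoint and objective.** The primary endpoint (Protocol 9.7.1.1.1) is "Change from baseline in the derived ADCOMS at 18 months of treatment in MCI/Prodromal subjects". The first primary objective (8.1) is the ED90 on that score at 18 months.
- **When success can be called.** Section 9.7.1.6 sets the criterion: at least 80% probability that the ED90 improves on placebo by 25% at 18 months. On timing it says that early success "can only be determined after at least 200 MCI/Prodromal subjects have been randomized". Section 9.7.3 adds: "Starting at the interim analysis for 200 subjects, the study will be monitored for success at each interim analysis". Looks come at every further 50 randomized up to 500, then every 3 months. The trigger is a count of randomized subjects, not of Month-18 outcomes.
- **What an interim success means.** Study success is at least an "80% probability of achieving 25% improvement over placebo at either an interim analysis or at the final analysis" (9.7.1.6). No further interim analysis follows an early success (9.7.3).
- **What happens afterwards.** Subjects already randomized go on to 18 months. In section 9.7.1.6.1, the second bullet in the list of additional Bayesian sensitivity analyses covers this situation: "the primary analysis as well as the above sensitivity analyses will be repeated after all subjects have completed 18 months of treatment". Anyone who drops out of contact before then counts as finished. The synopsis carries the same bullet under the same heading.
- **The conventional analysis is ordered the other way.** The same section describes final MMRM analyses and says that, with early success, they are also run on the data from before the interim. There the early cut is the addition.

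**The concern.** The protocol calls the Month-18 Bayesian analysis primary. After early success, it treats the version based on every subject's Month-18 follow-up as a check on the version based on the early look. Two things follow.

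First, an estimate taken at the moment a success threshold is first crossed tends to be too large, because the look was selected for being favourable. This does not depend on the exact share of missing outcomes.

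Second, with few observed Month-18 values spread over four arms, the dose identified as ED90 may change once the outcomes are in. Section 7 says the results guide both the move to Phase 3 and the choice of dose strengths, and that the study is meant to support registration. If the two analyses disagree, the protocol gives no rule for which effect and which ED90 are reported.

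**Working it through.** **1. The plan's own figure.** Section 9.7.2.1 reports simulated operating characteristics: at least 90% study success and at most 5% false claims. They cannot be reproduced from the protocol, which omits the placebo ADCOMS decline, its SD, the prior parameters, the longitudinal model and the accrual rate. Nothing below disputes them.

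**2. Share of subjects without a Month-18 value at a look.** The protocol gives no such share. It was derived from these inputs:
- Calendar: "The study will begin in Nov 2014 and is projected to end by Oct 2019" (9.1.2.3), so 59–60 months.
- Treatment 78 weeks = 17.95 months; follow-up 12 weeks = 2.76 months (9.1.2).
- Screening 2–3 months (9.1.1).
- Stage A about 32 months and Stage B about 42 months. These come from the earlier-version synopsis in the same file, because the start of the current synopsis is not shown.
- Stage A size 60 ± 20%, both cohorts together, with no fixed split (9.3). The MCI/Prodromal number is therefore an assumption: 15 to 72.
- Uniform accrual to 500 and no dropout (assumed).

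Formulas:
- Stage B accrual = 42 − screening − 17.95 − 2.76 = 18.3 to 19.3 months.
- Stage A accrual = 32 − screening − 17.95 − 2.76 = 8.3 to 9.3 months.
- Share lacking = 1 − (number randomized at least 78 weeks before the look) ÷ (number randomized at the look).

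Worked case (60-month calendar, 3-month screening, 30 MCI/Prodromal subjects in Stage A):
- Stage B opens at month 60 − 42 = 18 and first randomizes at month 21.
- Rate = (500 − 30) ÷ 18.3 = 25.7 per month.
- The 200-subject look falls at 21 + 170 ÷ 25.7 = 27.6 months.
- Subjects randomized by 27.6 − 17.95 = 9.65 months have reached Month 18: 30 × (9.65 − 3) ÷ 8.3 ≈ 24.
- Share lacking = 1 − 24 ÷ 200 = 88%.

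Ranges over the 59–60 month calendar and 2–3 month screening:

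| MCI/Prodromal in Stage A | 200 look | 250–450 looks | 500 look |
|---|---|---|---|
| 15 | 94–95% | 94–97% | 90–95% |
| 30 | 88–90% | 88–93% | 88–92% |
| 45 | 83–86% | 82–90% | 85–89% |
| 60 | 79–83% | 77–87% | 82–86% |
| 72 | 76–81% | 73–84% | 80–84% |

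The overall range is roughly 75–97%. The single lowest cell, 73%, needs all of an upper-limit Stage A (72) to be MCI/Prodromal. Stage B accrual is about as long as the endpoint itself, so until about full enrolment only Stage A subjects can have a Month-18 value.

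Quarterly looks after full enrolment: 66–79% lacking at +3 months, 53–63% at +6, 40–48% at +9, 26–32% at +12 and 13–16% at +15.

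Slower Stage B accrual (24–36 months assumed, 15–60 MCI/Prodromal in Stage A): 70–93% at the 200 look and 44–73% at the 500 look.

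**3. What complete data would add.** With 30 MCI/Prodromal subjects in Stage A, about 19–24 of 200 have a Month-18 value at the first success look. If the 20% attrition that 9.7.2.1 assumes for vMRI is borrowed, about 0.80 × 200 = 160 would have one at the end.

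**4. Direction of the change (illustrative).** One simulation took a placebo decline/SD ratio of about 1.0, back-solved from the mild to moderate AD power statement. It used an assumed dose-response prior, fixed 1:1:1:1 allocation and no futility stop. Its false-success rate was 1.4% under no effect.
- True effects 15/25/35%: the median estimated effect of the chosen dose went from 42% at the trigger to 38% on the same subjects' complete data. The ED90 changed in 17% of runs, and 31% no longer met the 80%/25% criterion.
- True effects 10/20/25%: 41% to 33%, 22% and 58%.

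A second rough simulation, with its own assumed priors and SD, gave about 42% to 37%, 14% and 27%.

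**The case against.** Several stronger readings are tempting, and the document does not support them.

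- **That the effect and the ED90 are fixed at the early look.** The protocol never says so. It repeats the analysis on complete data and is silent on precedence. What can be shown is the rank of the repeat and that silence.
- **That 90–95% of subjects lack the outcome.** No accrual rate or Stage A split is given. That figure needs about 30 or fewer MCI/Prodromal subjects in Stage A, and it does not apply to the quarterly looks, where early success can equally be declared.
- **That the early estimate is almost pure extrapolation.** Table 7 schedules the ADCOMS component scales at Months 3, 6, 9, 12 and 15, so many pending subjects contribute observed trajectories.
- **That the protocol provides a fill-in rule only for subjects censored for AChEI or memantine changes.** Further analytical detail is assigned to the SAP, due before the first interim efficacy analysis. This is not a defect of the protocol.
- **That the simulated sizes apply to this trial.** They omit response-adaptive randomization, which bears directly on ED90 selection, and the binding futility rule. In the 10/20/25% scenario the best true effect equals the 25% threshold, so losing the criterion is largely built in.

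Three further arguments deserve weight. In a Phase 2 proof-of-concept study, treating the decision-time analysis as primary is a defensible choice, and nothing stops the sponsor using the repeat for dose selection. Success is defined through the ED90's own posterior, so separating the two could leave success declared on one dose and the primary ED90 on another. Stopping enrolment may also signal success to sites while the clinician-rated CDR is still being collected.

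These points limit the size of the concern and call for both results to be shown together. They do not explain why the complete-data Bayesian answer to an 18-month objective should rank below the early one when the MMRM in the same section is ordered the opposite way.

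**Conclusion.** The point holds as one of ranking and precedence. Early success can be called with no minimum number of Month-18 outcomes, and the complete-data repeat is labelled a sensitivity analysis. No rule covers disagreement between the two.

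At enrolment looks, roughly 75–97% of MCI/Prodromal subjects would lack the endpoint value. This rests on the earlier-version durations, uniform accrual and an assumed Stage A split, and it is lower under slower accrual. At the later quarterly looks the share is about 13–79%.

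The upward bias at first crossing and the possibility of a changed ED90 follow from the design. Their sizes are not established, because the simulated figures rest on assumed priors, SD and fixed allocation. The change is worth making because it is cheap and the result drives dose selection.

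**What to change.** Leave the early-success rule as it is for stopping randomization and for declaring success. The simulated operating characteristics and the trigger for the mild to moderate AD interim looks are then untouched.

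Move the second bullet of the sensitivity list in 9.7.1.6.1, and its counterpart in the synopsis, out of that list and state:

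*If early success is declared, the primary estimate of the 18-month treatment effect and the primary ED90 are taken from all randomized MCI/Prodromal subjects once each has reached Month 18 or is lost to follow-up. The analysis at the time of early success is reported beside it as the interim decision analysis, with a statement of whether the ED90 and the 80%/25% criterion are unchanged.*

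The cost is wording in the protocol and, where needed, the SAP. No extra subjects, visits or analyses are required, because the repeat is already planned. The reported effect will usually be somewhat smaller, the definitive ED90 comes up to 18 months after the early call, and it may differ from the dose on which success was declared. The enrolment stop and early Phase 3 planning are not delayed.

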6 INVESTIGATORS AND STUDY PERSONNEL

This study will be conducted by qualified investigators under the sponsorship of Eisai (the sponsor) at approximately 35 investigational sites in the United States for Stage A and 125 sites globally for Stage B. (revised per Amendments 01, 02, and 04)

The name and telephone and fax numbers of the medical monitor and other contact personnel at the sponsor and of the contract research organization(s) (CRO[s]) are listed in the Investigator Study File or the Regulatory Binder provided to each site.

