Randomization and stratification will be used in this study to avoid bias in the assignment of subjects to treatment, to increase the likelihood that known and unknown subject attributes (eg, demographics and baseline characteristics) are balanced across treatment groups, and to ensure the validity of statistical comparisons across treatment groups ([Section 9.7.4](#)) Blinding to treatment will be used to reduce potential bias during data collection and evaluation of endpoints.

The rationale for the selection of doses used in the study is provided in [Section 9.4.4](#).

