9.7 Statistical Methods

All statistical analyses will be performed by the sponsor or designee. Statistical analyses will be performed using SAS software or other validated statistical software as required.

All statistical tests will be based on the 5% (2-sided) level of significance, except for the Bayesian methods on the primary endpoint.

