9.7.4 Other Statistical/Analytical Issues

Adaptive Randomization in the MCI/Prodromal Cohort

Randomization to placebo or 1 of 3 dose groups of E2609 will be fixed for the first 100 MCI/Prodromal subjects randomized in the study (1:1:1:1; placebo to each of the 3 active doses for the first 100 MCI/Prodromal subjects randomized, including those randomized from both Stage A and Stage B). Thereafter, randomization probabilities to each treatment group will be updated at each interim analysis, such that the randomization probability will be increased for the placebo group and dosage groups that represent the potential target dose (ED₉₀), and simultaneously decreased for other active arms. (revised per Amendment 01)

Randomization in the Mild to Moderate AD Cohort (revised per Amendment 01)

In Stage A, the mild to moderate AD subjects will be randomized to placebo or 1 of 3 E2609 dose groups (5, 15, and 50 mg of E2609) at a 1:1:1:1 ratio, while in Stage B, the mild to moderate AD subjects will be randomized to placebo or 1 of 2 E2609 dose groups (15 and 50 mg E2609) at a 1:1:1 ratio. (revised per Amendment 01)

Stratification (revised per Amendment 01)

Within the 2 clinical cohorts (MCI/Prodromal and mild to moderate AD), subjects will be stratified at randomization by *ApoE4* status (positive or negative) and prior treatment with AChEIs or memantine or both (yes or no). (revised per Amendment 01)

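### The named terms of the conventional ADCOMS MMRM omit allocation block although ratios change at each interim, so contrasts for de-emphasised doses can absorb enrolment drift

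*Protocol*

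**What the plan says.** Section 9.7.4 states: "Randomization to placebo or 1 of 3 dose groups of E2609 will be fixed for the first 100 MCI/Prodromal subjects randomized". After that, "randomization probabilities to each treatment group will be updated at each interim analysis". Placebo and the doses that look like the ED90 gain share together, and the other active doses lose share. Section 9.7.3 places the interims at 100 subjects and then every 50 to a maximum of 500.

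For the conventional ADCOMS analysis, section 9.7.1.6.1 says "The model will include treatment groups, randomization stratification variables (the presence or absence of ongoing treatment with AChEIs or memantine or both", with ApoE4 status and baseline ADCOMS completing the list. It adds "Other covariates such as adjusted hippocampal volume will be studied" and "These analyses will be performed as sensitivity analyses on the FAS as well as the PP set".

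Section 9.2.1 gives one purpose of randomisation and stratification as "to ensure the validity of statistical comparisons across treatment groups". Section 6 describes the study as running "at approximately 35 investigational sites in the United States for Stage A and 125 sites globally for Stage B".

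**The concern.** Once the ratio differs between blocks, a subject's chance of receiving each arm depends on when that subject entered, so block acts as a stratum of the randomisation. The MMRM adjusts for the two variables used to stratify, but not for the one along which the ratio itself changes. Its contrasts are then free of drift bias only if outcomes do not change over enrolment, beyond what baseline ADCOMS, ApoE4 and AChEI/memantine use absorb.

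A dose that loses share keeps mostly early entrants, while placebo gains later ones. If later entrants decline more slowly, that dose looks worse than placebo with no drug effect behind it. The first primary objective (section 8.1) is to establish the ED90 across three doses, so distorted contrasts for the weaker-looking doses blur the dose-response picture. The MMRM is also the conventional check on the Bayesian result and should not carry an avoidable weakness of its own.

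**Working it through.** **What can be reproduced.** Section 9.7.2.1 gives a simulated false-claim rate of at most 5%, but for the Bayesian rule. It cannot be reproduced here, because the ADCOMS SD, priors, longitudinal model and allocation algorithm are not in the protocol. No error rate under drift is stated. For the MMRM the only figure is the general level in section 9.7: "All statistical tests will be based on the 5% (2-sided) level of significance, except for the Bayesian methods on the primary endpoint".

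**Assumptions.** Residual SD 1; no dose effect; 500 subjects in blocks of 100 + 8 × 50; outcome drifting linearly by D over enrolment (time 0 to 1); no early stopping; least squares at month 18 standing in for the MMRM.

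**Fixed-share calculation.** The first 100 subjects (25 per arm) have mean entry time 0.1, and the other 400 have mean 0.6. An arm with later share q has n = 25 + 400q and mean time m = (25 × 0.1 + 400q × 0.6)/n. Two de-emphasised doses take share s each; placebo and the target dose take (1 − 2s)/2 each. Then:

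- bias = D × (m_placebo − m_dose)
- SE = √(1/n_placebo + 1/n_dose)
- z = bias/SE
- two-sided rejection = Φ(−1.96 + z) + Φ(−1.96 − z)

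Example with s = 0.05: placebo n = 205, m = 0.539; dose n = 45, m = 0.322; difference 0.217. At D = 0.25 the bias is 0.054 SD, SE = 0.165 and z = 0.33, giving 6.3%.

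| Later share of the dose | D = 0.25 SD | D = 0.5 SD |
|---|---|---|
| same as placebo (target dose) | 5.0% | 5.0% |
| 15% | 5.2% | 5.8% |
| 10% | 5.5% | 7.2% |
| 5% | 6.3% | 10.1% |
| dropped after subject 100 | 8.2% | 18.4% |

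**Adaptive simulation.** Allocation follows the probability of being the ED90, with placebo either matched to the best dose or held at 35%. Lag is the number of blocks by which outcome data trail (6,000 trials per cell). The table shows two-sided rejection per comparison when later entrants decline less by 0.25 SD.

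| Lag (blocks) | No drift | Drift, no block term | Drift, block term |
|---|---|---|---|
| 0 (matched placebo only) | 6.3% | 11.3% | 7.4% |
| 2 | 5.4% | 9.2-9.4% | 6.2-6.4% |
| 4 | 4.8-5.1% | 7.3-7.4% | 5.2-5.7% |
| 6 (matched placebo only) | 5.1% | 6.1% | 5.3% |

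Other results:

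- With drift of 0.25 SD the other way, the unadjusted rate falls to 2.6-4.6%.
- At ±0.25 SD, false benefit for any dose is 4.3-7.2%, against 3.9-6.1% without drift.
- The comparison for the most-allocated dose rejects in 4.3-6.9%, against 4.6-6.2% without drift.
- Doubling generally needs about 0.5 SD towards slower decline (11-20% with lag 0 to 4; 8.2% with lag 6), and nearly all of that excess is false harm in de-emphasised doses.
- With the block term the rates do not move with drift. What remains above 5% comes from the adaptation itself.

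**How large is 0.25 SD?** Section 9.7.2.2 gives about 80% power with 200 mild to moderate AD subjects for reductions of 33% and 50%. Under two-sided Dunnett with 67 down to 53 evaluable per arm, that implies a placebo change of about 1.0 to 1.15 SD. On that scale, borrowed from the other cohort, 0.25 SD is 0.25/1.15 to 0.25/1.0, or 22-25% of placebo decline. That is about the size of the 25% improvement the trial targets.

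**The case against.** The ADCOMS MMRM is a sensitivity analysis; study success is decided by the Bayesian rule (section 9.7.1.6). Its covariate list is left open, and an SAP not shown may add terms. This limits the consequence. But a statement that other covariates will be studied does not commit to block, and the terms that are named leave it out.

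The visible sources of drift fall early. Stage A is at most 60 × 1.2 = 72 subjects across both cohorts, and Stage B keeps equal allocation until 100 MCI/Prodromal subjects are in, so the move from US to global sites happens inside the equal-allocation block. The memory criterion was loosened in Version 4.0, while Stage A was still running. This dilutes the contrast between the first block and later ones, and no drift size appears in the protocol. It weakens the case for a large effect without removing the mechanism.

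A reader might infer that any modest drift at least doubles the false-signal rate. The documents do not support that: the result depends on the sign of the drift and the speed of adaptation, an 18-month endpoint makes near-instant adaptation unlikely, and placebo rises with the target dose. Nor should the rates be read as two-sided Dunnett error. No Dunnett test is stated for this MMRM, and the null of no difference from placebo in section 9.7.2.1 belongs to the one-sided hippocampal-volume test, where false harm cannot reject. Section 9.7.1.6.2 lists no covariates for that model, so there the point asks for a specification and does not correct an error.

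**Conclusion.** The concern holds in a limited form. Allocation depends on block, the named MMRM terms omit block, and contrasts for de-emphasised doses can be biased if rate of decline drifts over enrolment. At 0.25 SD towards slower decline, the two-sided error per comparison goes from about 5% to about 6-9% with data trailing by two to six blocks. These figures rest on the assumed drift, allocation rule and lag, none of which the protocol gives. The distortion is mainly apparent harm in doses already losing share. It does not show that the success criterion or the target-dose comparison is compromised, and it gives no ground for changing the Bayesian primary model, whose stated operating characteristics would then need re-simulating.

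**What to change.** In section 9.7.1.6.1, add allocation block (first 100 subjects, then each interim block of 50) as a fixed categorical covariate in the sensitivity MMRM on ADCOMS. Name the same term for the MCI/Prodromal hippocampal-volume MMRM in section 9.7.1.6.2. Leave the Bayesian primary model as it is.

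Block is already known from the randomisation system. Nine blocks cost up to 8 degrees of freedom. In simulation the standard error rose by at most 2.3%, so intervals widen by about 1-2%.
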